Number of outpatient visits in the 180 days prior	Patient Characteristics	
Count unique days with an outpatient visit in the 180 days prior to index
 
 • Dichotomous, yes/no • Continuous statistics including mean, standard deviation (SD), median (Q1-Q3), minimum, and maximum. 
Model specification: number categories (0, 1, 2, 3+)

Number of hospitalizations in the 180 days prior	Patient Characteristics	
Count of unique days with an acute hospital admission (POS = 21 and tos_cd = 'FAC_IP.ACUTE') in the 180 days prior to index
 
 • Dichotomous, yes/no • Continuous statistics including mean, standard deviation (SD), median (Q1-Q3), minimum, and maximum 
Model specification: number categories (0, 1, 2+)

Number of prior COVID-19 tests in the prior 365 days	Patient Characteristics	
Count of unique days with COVID-19 test (PCR or antigen test) ordered in the 365 days prior to index
 
 • Dichotomous, yes/no • Continuous statistics including mean, standard deviation (SD), median (Q1-Q3), minimum, and maximum 
Model specification: number categories (0, 1, 2+)

Flu test in the prior 365 days	Patient Characteristics	
Influenza test ordered in the 365 days prior to index
 
 • Dichotomous, yes/no 
Model specification: dichotomous (yes/no)

Number of prior telehealth visits in the prior 365 days	Patient Characteristics	
Count of unique days with telehealth visit in the 365 days prior to index
 
 • Dichotomous, yes/no

PFIZER CONFIDENTIAL

Table 4. Covariates		
Variable	Role	Operational definition
		
 Continuous statistics including mean, standard deviation (SD), median (Q1-Q3), minimum, and maximum 
Model specification: number categories (0, 1, 2+)

Number of labs ordered in the prior 365 days	Patient Characteristics	
Count of unique days with any lab ordered in the 365 days prior to index
 
 Dichotomous, yes/no Continuous statistics including mean, standard deviation (SD), median (Q1 -Q3), minimum, and maximum 
Model specification: number categories (0, 1, 2+)

Prior COVID-19 infection	Patient Characteristics	
1 ICD-10-CM code (U07.1) in the 1 year baseline in any setting (>3 months prior to reflect exclusion criteria
 
Model specification: dichotomous (yes/no)

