9.7. Data Analysis

There is not a separate Statistical Analysis Plan document for this study. All methodology for summary and statistical analyses of data collected in this study is contained in this section. All computations and generation of tables will be performed using Statistical Analysis System (SAS) version 9.4 or higher (SAS Institute, Cary, NC, US).

All analyses will be conducted for the following age subgroups: 18-64 and 65+.

Descriptive statistics will be presented to describe baseline characteristics by vaccination exposure group. Baseline characteristics will be described by frequency distribution for categorical variables while continuous variables expressed in terms of their mean and standard deviation or median and interquartile range (IQR) as appropriate. In general, missing or unavailable data will not be imputed and data will be analyzed as they are recorded in the database.

To account for imbalance in patient characteristics between the vaccine exposure groups, 2 separate logistic regression models will be used to create a propensity score used to calculate an inverse probability of treatment weights (IPTW). The two models will be as follows: Same day vs COVID-19 alone, and separately Same day vs Flu alone. Weights will be stabilized to avoid exertion of outliers, and we will further evaluate whether there is a need to truncate at the 1st and 99th percentile. Covariate balance before and after weighting will be assessed using standardized mean differences, separately for the same day/COVID-19 alone and Same day/flu alone comparisons. All variables listed in “[Covariates](#)” section with model specification instructions will be included in the score. If there are model convergence issues, changes in model specification may occur (eg, dropping variables with very low prevalence, categories may be collapsed further etc). Variables with residual imbalance will be included in the model for further adjustment.

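### Visit, lab and telehealth counts enter the propensity scores with low open-ended top categories, so some confounding by intensity of care can remain, and the balance check is not required to look for it

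*Combined protocol and SAP*

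**What the plan says.** Table 4 in Section 9.3.4 defines the outpatient variable as a full count: "Count unique days with an outpatient visit in the 180 days prior to index". It plans "Continuous statistics including mean, standard deviation (SD), median (Q1-Q3), minimum, and maximum" for that count. The form used in the score is "Model specification: number categories (0, 1, 2, 3" or more). Laboratory use is handled in the same way. The variable is "Count of unique days with any lab ordered in the 365 days prior to index", and its score form is "Model specification: number categories (0, 1, 2" or more). Telehealth days and COVID-19 tests (365 days) and hospitalizations (180 days) have the same three levels. Age, by contrast, is modelled as continuous.

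Section 9.7 states that all Table 4 variables "with model specification instructions will be included in the score". On diagnostics it says: "Covariate balance before and after weighting will be assessed using standardized mean differences". It then adds: "Variables with residual imbalance will be included in the model for further adjustment". It gives no threshold for imbalance. It also does not say whether a count is checked in its category form or as the raw number.

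**The concern.** A patient with 3 outpatient days in six months and one with 20 look the same to the score through this variable. The same holds for 2 lab days and 15. If same-day recipients and single-vaccine recipients differ in how far above the cap they sit, and risk keeps rising with use, weighting on the categories leaves that difference in place. The outcomes exposed are those that depend on illness burden or care-seeking: all-cause hospitalization, the COVID-19 and influenza composites, and the outpatient endpoints.

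Section 9.5 sizes the study on a hazard-ratio margin of 1.15 with an expected ratio of 1. Against that yardstick a bias of a few per cent matters, and groups of this size give narrow intervals that will not absorb it. The risk is greatest at 65+, where more patients are likely to be in the top categories, although the documents do not show this.

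**Working it through.** **The plan's own figure.** The documents give no figure for residual confounding, so the check starts from the sizing that sets the scale. Events needed = (1.960 + 0.842)² / [0.63 × 0.37 × (ln 1.15)²] = 1,724, as Section 9.5 states for the 65+ COVID-19 composite. With 23% in Group 1 the formula gives 2,269, also as stated. Table 5 with the 0.56% event rate implies (382,806 + 225,842) × 0.0056 ≈ 3,408 events.

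**Base case, outpatient days only (all inputs except the 63% allocation are assumptions).** Outpatient days are negative binomial with mean 6 and dispersion 1.2. The odds of same-day vaccination fall 2% per visit, the outcome rate rises 3% per visit, and the true HR is 1. The ratios are exact sums over the count distribution.

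- Share with 3 or more days: 66%. Group means: 5.7 (same day) and 6.5.
- Crude ratio: 0.974.
- After weighting on 0/1/2/3+: 0.982. Share of log bias left, from unrounded ratios = ln(0.9823)/ln(0.9742) = 68%.
- After weighting on 0/1/2/3-5/6-9/10-14/15+: 0.996, with 14% left.
- After the planned weighting, the category differences are zero and the raw-count standardized mean difference is -0.077.
- With mean 4 to 6, exposure slope 1-3% and outcome slope 2-5%, the bias left by the planned categories runs from 0.2% (ratio 0.998) to about 5% (ratio 0.948).
- If risk levels off at 10, 6 or 3 visits, the share left falls to 46%, 27% and 0%.

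**Other levels of use (exact calculation, one capped count, same-day mean 0.8 times the comparator, no plateau).** For outpatient days, 9-24% remains at mean 1.5, 25-45% at mean 3, 41-58% at mean 5 and 52-71% at mean 8. For lab days, 13-27% remains at mean 1 and 57-75% at mean 6. With a plateau at 3 days, 0% remains for outpatient days and 8-18% for labs.

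**More of the planned score (simulation, 100,000 patients per scenario).** The score held the outpatient, lab, hospitalization and telehealth categories plus Charlson 0/1/2+. The share of confounding left when the visit count itself drives it, for a logarithmic and a linear risk gradient, was:

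| Use level | Share with 3+ outpatient days | Logarithmic | Linear |
|---|---|---|---|
| Low | 20% | 15% | 23% |
| Middle | 40% | 28% | 41% |
| High | 61% | 44% | 57% |
| Very high | 69% | 48% | 60% |

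The difference in the 3+ share after weighting was at most 0.0005, while the raw-count standardized mean difference was 0.08-0.17 in absolute value. When a latent intensity of care drove the confounding, 34-44% was left and the raw-count difference was 0.02-0.07.

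Adding raw and log outpatient and lab counts to the score brought the count-driven residual to between -2% and 1%, and the latent-driven residual to 18-35%.

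**Consequence against the 1.15 margin.** SE of log HR = 1/√(1,724 × 0.63 × 0.37) = 0.0499. With residual bias b, the chance of declaring non-inferiority at a true HR of 1.15 is Φ(-ln b/SE - 1.96).

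- b = 0.982: Φ(0.364 - 1.96) = 5.5%, against the nominal 2.5%.
- b = 0.96, near the upper end of the range: Φ(0.818 - 1.96) = 12.7%, or 20.9% with 3,408 events.
- b = 1/0.96: power at HR 1 falls from 80% to 51% with 1,724 events.

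**The case against.** The strongest reply is that the caps do not act alone. The score also holds Charlson index, immunocompromise, risk conditions, nursing-home and skilled-nursing stays, functional status, wellness visits, tests and age, and all of these are likely to track intensity of care. The 68% comes from a score with a single covariate. It passes half in the fuller simulation only with high use, a linear gradient and count-driven confounding, and even that simulation omits several planned covariates. A reader might infer from the base case that most of the confounding survives weighting; the documents do not support that. They give no count distribution and no gradient, and a plateau near the cap removes the outpatient problem. The base-case bias is also small: 0.018/0.050, about a third of one standard error at 1,724 events.

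A reader might also infer that the balance table is bound to look clean. Section 9.7 does not say so. Table 4 already plans means and SDs of these counts, so a raw-count check is compatible with the text, and variables found unbalanced are to be adjusted for further. Section 9.3.2 adds three negative control outcomes chosen because they are expected to share confounding by health-seeking.

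All of this limits the size of the point, but none of it changes the score. Charlson is itself capped at 2+, and the risk-condition variable is one yes/no. The separate pneumonia, heart, asthma, lung, diabetes and kidney rows carry no model specification, so by the Section 9.7 rule they appear to be outside the score. The continuous summaries are planned as baseline description, with nothing said about weighting. Further adjustment acts only on imbalance that is seen, and the negative controls can flag bias but not remove it.

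**Conclusion.** The point holds as a weakness in model specification, of moderate and uncertain size. The planned categories cannot remove group differences above 3 outpatient days or 2 lab or telehealth days through these variables, so some confounding by intensity of care can remain, mainly at 65+. Under the assumed distributions, 15-60% of count-driven confounding is left when the count categories and Charlson are in the score. In the single-covariate base case this is an HR bias of about 2% (range 0.2-5%). Its direction depends on which group uses more care, which the documents do not give. Whether the imbalance would be noticed is open, because Section 9.7 leaves the form of the balance check unstated.

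**What to change.** In Table 4, change the model specification for outpatient, lab and telehealth counts to finer categories (for example 0, 1, 2, 3-5, 6-9, 10-14, 15+) or to log(1+count) with a restricted cubic spline. In Section 9.7, state that post-weighting standardized mean differences and variance ratios will be reported on the raw counts, and give the threshold that triggers further adjustment. A mean difference alone may not be enough: the base-case value of -0.077 would pass a cut-off of 0.1 (an assumed figure, since the plan gives none), so the score form should change as well as the diagnostic.

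The counts are already derived. The cost is a few extra parameters per score, which is negligible when the smallest group in Table 5 has 144,695 patients. The change will not remove confounding by aspects of illness that the counts measure only indirectly.

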9. RESEARCH METHODS

9.1. Study Design

[figure not shown]
This structured secondary data collection study will be a retrospective, cohort design to describe concomitant vaccine uptake and subsequent outcomes during one influenza vaccination season. Individuals will be indexed on the date of their first Pfizer-BioNTech mRNA bivalent COVID-19 or influenza vaccine. Exposure groups will be assigned as follows:

- Group 1: Same day (Pfizer-BioNTech mRNA bivalent COVID and flu on the same day);
- Group 2: COVID alone (Pfizer-BioNTech bivalent COVID only);
- Group 3: flu alone (influenza vaccine of any type only).
- CCI

A one year lookback period prior to the index vaccination will be used to identify covariates. Individuals will be followed starting 15 days after vaccination until experiencing one of the following: 1) outcome 2) disenrollment 3) receipt of a second vaccine of the same type 4) receipt of the other vaccine or any type of COVID-19 vaccine 5) end of data or 6) death. Only Pfizer-BioNTech mRNA bivalent COVID-19 vaccine will be assessed. All types of influenza vaccines recommended for the eligible population will be eligible for inclusion, but for the 65+ age group only enhanced influenza vaccines will be included.

PFIZER CONFIDENTIAL

Figure 1. Overall Study Design

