9.2.1. Inclusion Criteria

Patients must meet all of the following inclusion criteria to be eligible for inclusion in the study:

1. Enrolled in Optum claims database as of 31 August 2022 (date bivalent authorized).
2. Has a Pfizer-BioNTech mRNA bivalent COVID-19 or influenza vaccine (any type) between 31 August 2022 and 30 January 2023 (earliest vaccine is index date).
3. Aged ≥ 18 years on the index date.
4. 365 days of continuous enrolment prior to index date.

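### Both propensity scores count acute admissions and outpatient days over 180 days only, so days 181-365 of an observed one-year baseline go unadjusted and unchecked for balance

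*Combined protocol and SAP*

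**What the plan says.** Section 9.1 sets the general rule: "A one year lookback period prior to the index vaccination will be used to identify covariates". Inclusion criterion 4 in section 9.2.1 requires "365 days of continuous enrolment prior to index date", so the full year is observed for everyone.

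Table 4 in section 9.3.4 then gives the hospitalization covariate, "Number of hospitalizations in the 180 days prior", a shorter window: "Count of unique days with an acute hospital admission (POS = 21 and tos_cd = 'FAC_IP.ACUTE') in the 180 days prior to index". It enters the model as 0, 1 or 2+. The row "Number of outpatient visits in the 180 days prior" also uses 180 days, in categories 0, 1, 2 and 3+. The other utilization rows use 365 days: COVID-19 tests, influenza tests, telehealth, laboratory orders, wellness visits, nursing home and skilled nursing facility (SNF) claims. No reason is given for the difference.

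Section 9.7 says that "2 separate logistic regression models will be used to create a propensity score", one for Same day versus COVID-19 alone and one for Same day versus Flu alone. Covariates "with model specification instructions will be included in the score", so the 180-day counts enter both scores. Balance is judged by standardized mean differences, and variables that stay imbalanced are added to the outcome model.

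**The concern.** The hospitalization covariate is the lagged form of an endpoint. All-cause hospitalization in Table 2 uses the same place-of-service and acute-facility codes plus a confinement identifier. It is named in Primary Objective 2 and modelled in both comparisons. A patient admitted seven months before index gets a 0 on this row, the same value as a patient with no admission in the year.

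If the vaccine groups differ in admissions on days 181-365 after weighting, and those admissions predict later hospitalization given the rest of the score, the difference passes into the HR. The planned diagnostics would not show it. Balance is assessed on the listed covariates, so the rule for adding imbalanced variables cannot be triggered by a period that no row records.

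**Working it through.** **1. Window.** Observed baseline is 365 days (section 9.2.1) and counted baseline is 180 days (Table 4). 365 - 180 = 185 days unused; 185/365 = 50.7%.

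**2. What else in the scores covers days 181-365.** Full-year rows with a model specification include:
- the comorbidity index, as 0/1/2+;
- one yes/no flag for any high-risk condition, on a list that includes hypertension and overweight;
- one yes/no flag for immunocompromise;
- nursing home and SNF claims;
- functional status;
- prior COVID-19 infection (more than three months back) and prior influenza infection.

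These pick up diagnoses and post-acute care linked to an earlier admission. None records an acute admission as such. The separate one-year rows for pneumonia or respiratory failure, heart disease, asthma, chronic lung disease, diabetes and kidney disorders carry no model specification, so under section 9.7 they do not enter the scores.

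**3. The plan's own figures.** The non-inferiority margin of 1.15 in section 9.5 gives a scale. Schoenfeld events = (1.96 + 0.8416)² / [q(1 - q)(ln 1.15)²], where q is the share in Group 1.
- 65+ COVID-19 composite, q = 0.63: 7.849 / (0.2331 × 0.01953) = 1,724, as stated.
- 65+ influenza composite, q = 0.23: 7.849 / (0.1771 × 0.01953) = 2,269, as stated.

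These figures reproduce, and they do not depend on the covariate window.

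**4. Illustrative bias.** The documents give no admission frequency for days 181-365, no hazard ratio for it and no residual imbalance. All three are assumptions here:
- p0 = 3% or 6% of the comparator group admitted only on days 181-365;
- the Same day group lower by d = 0.5 to 2 percentage points after weighting, p1 = p0 - d;
- a conditional hazard ratio R of 1.5 to 3 for such patients.

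Factor on the HR = [1 + p1(R - 1)] / [1 + p0(R - 1)].

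| p0 | d | R = 1.5 | R = 2 | R = 3 |
|---|---|---|---|---|
| 3% | 0.5 | 0.9975 | 0.9951 | 0.9906 |
| 3% | 1 | 0.9951 | 0.9903 | 0.9811 |
| 3% | 2 | 0.9901 | 0.9806 | 0.9623 |
| 6% | 0.5 | 0.9976 | 0.9953 | 0.9911 |
| 6% | 1 | 0.9951 | 0.9906 | 0.9821 |
| 6% | 2 | 0.9903 | 0.9811 | 0.9643 |

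The shift runs from about 0.2% to about 4%. On the log scale, with ln 1.15 = 0.1398, that is 0.0024/0.1398 = 2% to 0.0384/0.1398 = 27% of the margin. If the Same day group has more such admissions, the shift goes the other way; for example, p0 = 3%, d = 2 and R = 3 give (1 + 0.05 × 2)/(1 + 0.03 × 2) = 1.038.

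**5. Upper bound check.** With p0 = 5% and R = 3, a bias as large as 1.15 needs p1 = [1.15 × (1 + 0.05 × 2) - 1]/2 = 13.25%. An imbalance of 13% against 5% after weighting is far outside the assumed range.

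**The case against.** The strongest reply is that 180 days is a legitimate recency window and that the scores already hold much of the earlier history. A good part of this stands, and it rules out several stronger readings that a reader might infer.

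- *That Table 4 contradicts section 9.1.* It does not. A one-year lookback need not be used in full by every covariate. The 180 days are written into the variable's name, and other rows also use part-year windows: prior influenza vaccination has fixed calendar dates, and prior COVID-19 infection excludes the last three months.
- *That half of the most important prognostic history is lost.* The 51% is a share of days. The documents rank no covariate and do not show that days 181-365 carry as much information as the latest 180.
- *That a patient admitted earlier is weighted as if never admitted.* The full-year rows in step 2 also shape the weight, so this patient is treated as unadmitted on one row only.
- *That the loss of winter admissions is a defect in itself.* The window opens between 4 March and 3 August 2022, so no admission from December 2021 to February 2022 counts. But coded COVID-19 and influenza infections from that winter within the one-year baseline do enter. A 365-day window would not restore the whole winter either: for an index date of 30 January 2023 it starts on 30 January 2022.
- *That the false-positive rate for non-inferiority is inflated by a known amount.* Such a figure needs an assumed shift in an assumed direction. The margin appears only in section 9.5; the visible text of section 9.7 plans HRs with 95% CIs and no non-inferiority decision rule.

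The three negative control outcomes in section 9.3.2 are a partial safeguard, especially hospitalization on days 1-14. They may signal residual confounding, but they do not locate its source, and the visible text attaches no corrective step.

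None of this explains why 180 days was chosen, and none of it supplies a count of admissions on days 181-365.

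**Conclusion.** The point holds as an unexplained analysis choice that leaves avoidable residual confounding. Acute admissions and outpatient days from 185 of 365 observed days are absent from both scores and invisible to the balance check, and the remaining full-year covariates stand in for them only in part. It matters most for all-cause hospitalization.

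The size and direction of any bias cannot be derived from the documents. The range of about 0.2% to 4% on the HR rests wholly on the prevalences, residual differences and hazard ratios assumed above. Recent admissions, comorbidity and facility stays are correlated with earlier admissions, so the true shift is probably toward the low end. No sample size, event count or power figure in section 9.5 changes.

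**What to change.** In Table 4, keep the 0-180 day counts, which preserve recency, and add two rows: acute hospitalizations on days 181-365 before index (0, 1, 2+), and outpatient days on days 181-365 in the categories already used for the recent count. Give each a model specification so that it enters both propensity scores, and report its standardized mean difference before and after weighting in both comparisons.

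The cost is two lines in Table 4 and five extra indicator terms per score (two for hospitalizations, three for outpatient days with 0, 1, 2, 3+). By Table 5 the smallest model, ages 18-64 for Same day versus COVID-19 alone, has 244,864 + 144,695 = 389,559 patients, and section 9.7 already allows categories to be collapsed if a model fails to converge. The claims fall within the required enrolment period, so no new data are needed and no patients are lost.

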9.4. Data Sources

Optum's Clininformatics Data Mart (CDM) comes from a database of administrative health claims for members of a large national managed care company affiliated with Optum. The database includes over 73 million unique lives (2007 through 2021). Clininformatics Data Mart is statistically de-identified under the Expert Determination method consistent with HIPAA and managed according to Optum customer data use agreements. These administrative claims submitted for payment by providers and pharmacies are verified, adjudicated, adjusted, and de-identified prior to inclusion. The Claims data comprises both commercial/employer sponsored plans and Medicare Advantage health plan data. This data covers ~30% of the national Medicare Advantage population. The population is geographically diverse, spanning all 50 states. In addition to medical claims and pharmacy claims, the Claims data includes tables with member eligibility and inpatient confinements. The Claims data also includes standard pricing for all medical claims, pharmacy claims, and inpatient confinements. Mortality is provided as month and year of death and is sourced from Centers for Medicare and Medicaid Services, Social Security Administration Death Master File, facility claims with inpatient death, discontinuation of coverage due to death and external obituary data.

